Intraligamentary Anaesthesia is delivered manually via conventional, or high-pressure syringes,⁽²⁷⁾ or using computer-controlled local anaesthetic delivery systems (CCLADS).⁽²⁸⁾ There are some potential problems with the conventional intraligamentary technique. One such problem is the high pressure required to inject the anesthetic solution, which may lead to breakage of the glass cartridge with a conventional syringe.⁽²⁹⁾

The Wand-STA Single Tooth Anaesthesia is a CCLADS launched in 2006 by the manufacturers of the Wand Compudent system.⁽³⁰⁾ It's the only delivery system with incorporated dynamic pressure sensing (DPS) technology to monitor real-time pressure.⁽³¹⁾ It is capable of identifying the periodontal ligament tissue and enables the clinician to maintain the correct needle position within the periodontal ligament when performing ILA. Developed by [name], the STA-Intraligamentary Injection represents a new concept in local dental anesthesia techniques.⁽³²⁾

The system is activated by a foot control that allows a more precise and accurate LA delivery at a decreased steady pressure and volume via the intraligamentary route, regardless of the tissue resistance. This helps reduce tissue distortion and thus potentially minimizing the painful experience of ILA. However, it is significantly more expensive than a PDL-syringe and handling of the STA system may be complex for less trained dentists.⁽³³⁾

Garret-Bernardin and Cantile (2017)⁽³⁴⁾ showed that computerized injections are better tolerated and reduced pain perception in 7 – 15 year old patients compared to the traditional syringe during routine dental treatment.⁽³⁵⁾ In another study conducted on primary teeth, Tekin and Ersin (2012)⁽³⁶⁾ reported that a significantly higher mean Sound, Eye and Motor (SEM) score of pain reaction for IANB group was recorded in comparison to conventional ILA during both injection and extraction periods of mandibular primary teeth ($p < 0.005$).

Various studies report adequate anesthesia with computer controlled intraligamentary injection for primary tooth cavity preparation and pulpectomy as well as permanent tooth extraction.^(29, 33, 37-39) However, limited studies have been conducted to evaluate the efficacy of computer-controlled-ILA (CC-ILA) for extraction of primary molars.⁽³⁰⁾

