The sample size was calculated based on results obtained from previous studies of similar nature. Sample size was estimated assuming alpha error= 5% and study power= 80%. Tekin et al ⁽³⁶⁾ reported mean \pm SD Sound, Eye and Motor (SEM) score = 3.93 ± 1.223 when intraligamentary anesthesia (ILA) was used, and 5.17 ± 1.891 when inferior alveolar nerve block (IANB) was used. Based on comparison of means, sample size was calculated to be 25 per group, and the total sample size required to compare the effectiveness of CC-ILA technique versus IANB during extraction of primary mandibular molars = number of groups \times number per group= $2 \times 25 = 50$.⁽⁴¹⁾ The sample size was calculated using powerandsamplesize.com calculator.⁽⁴²⁾

Criteria for sample selection:

a) Eligibility Criteria

- Age range from 5 – 7 years.
- Children free of any systemic disease or special health care need (ASA I).⁽⁴³⁾
- No previous bad dental experience.⁽⁴⁴⁾
- Positive or definitely positive behaviour during preoperative assessments according to the Frankl Rating Scale (score 3 or 4) (Appendix I).⁽⁴⁵⁾

- Patients whom their mandibular primary molars are indicated for extraction:^(46, 47)
 - Clinical signs and symptoms of pulp degeneration, such as swelling or sinus tracts.
 - Radiographic evidence of periapical or interradicular radiolucency.
 - Non restorable crowns.
 - Failed pulpotomies.
- Patients whose parents will give their consent to participate.

b) Exclusion Criteria for teeth ⁽⁴⁸⁾

- Root resorption affecting more than one third of the root length.
- Fractured roots due to trauma.
- Signs of mobility.
- Ankylosed roots.
- Active sites of pathosis in area of injection that could affect anaesthetic assessment.
- History of allergy to local anesthesia.

Materials

- a) Topical Anaesthesia – Benzocaine gel 20%.*
- b) 27-guage long anaesthetic needles.**
- b) Local anaesthetic carpules: Articaine hydrochloride 4% with adrenaline 1:100,000.***
- c) Equipment:
 - Wand - STA Single Tooth Anaesthesia Device (Figure 2)****
 - Disposable Wand – STA Handpieces with 30-guage 0.5-inch needles. ****
 - Pulse oximeter.*****
 - Dental anaesthetic syringe (non-disposable breech loading, metallic cartridge type).*****
 - Lower Full-crown Extraction forceps.*****

* Dharma Research, Inc. [name].

** C-K Ject, CK Dental Ind. Co., LTD., Korea.

*** ARTINIBSA, Inibsa Dental S.L.U, [name].

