- The operator will wait for 3-5 minutes before commencing dental treatment. Numbness will be tested with a dental probe on the gingiva immediately following the injection, and after each 10 seconds in case of CC-ILA and each 30 seconds in case of IANB till full numbness is declared and the time of onset of the anaesthetic effect will be noticed.
- In both groups, extraction will be accomplished according to AAPD guidelines.⁽⁵⁶⁾ Lower full crown forceps will be used to apply slow continuous palatal/lingual and buccal force allowing for the expansion of the alveolar bone to accommodate the divergent roots and reduce the risk of root fracture.
- Care will be taken to support the mandible with the non-extraction hand.
- If the patient suffered pain at any given time in the experimental group, the procedure will be abandoned immediately, IANB will be administered, and extraction will be carried out.

- Post extraction instructions will be given to the patient. They will be instructed to bite on gauze with firm pressure against the surgical site for 30 minutes. They should not disturb the surgical site or rinse vigorously on the day of extraction. According to the technique used, avoid scratching, or injuring the cheek, lips, or tongue if numbness is felt. They should avoid any physical exercise on the day of extraction. Cold soft food is recommended, as well as drinks to keep the child hydrated but without using a straw.
- Analgesics and/or antibiotics will be prescribed if required.
- Planning for space maintenance will be considered as well. All dental injections and extractions will be administered by the same operator, who will be assisted by a trained dental assistant.

Follow up

Following extraction, follow up after 24-hours will be planned via telephone calls to assess any adverse events.

Study Outcomes

I. Assessment of Child Pain Reaction

In the present study, pain will be assessed using the following 3 methods:

A. Physiologic method:

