Heart rate (HR) is a physiological sign of pain.⁽⁵⁷⁾ It will be measured using a pulse oximeter. A brief demonstration using the pulse oximeter will be done, and the patient will be instructed to stay still and not to move his hands a lot in order to obtain accurate readings. The pulse oximeter will be placed on the patient's index finger to measure the baseline heart rate (before giving the LA), another measurement will be recorded during LA administration, and during extraction. Readings will be recorded at 2-minute intervals and the mean heart rate measurement will be calculated.

B. Objective method:

Sound, Eye, Motor (SEM) Scale (Figure 3), will be used as an objective method for pain assessment during LA administration and extraction. It comprises the following parameters: (1) Sound, (2) Eye, (3) Motor. For each child, the sounds, eye symptoms and body movements will be evaluated independently by a blind impartial observer using the recorded video tapes. The slightest manifestation of the sound, eyes, or motion of the patient is graded in four levels: comfort, mild, moderate, and severe discomfort, and subsequently given grades 1, 2, 3, 4, respectively. SEM score will be calculated by summing the three grades of the parameters. ⁽⁵⁸⁾

Parameter	Comfort	Mild discomfort	Moderate discomfort	Severe discomfort
Grade	1	2	3	4
Sound	No sound	Non-specific sound (probable pain)	Verbal complaint, louder sound	Verbal complaint shouting, crying
Eye	No sign	Dilated eye without tears (anxiety sign)	Tears, sudden eye movements	Crying, tears all over the face
Motor	Relaxed body and hand status	Muscular contraction, contraction of hands	Sudden body and hand movements	Hand movements for defence, turning the head to the opposite side

Figure (3): SEM scale for the assessment of children's behaviour

Subjective method:

A modified face scale⁽⁵⁹⁾ (Figure 4) from the Maunuksela et al⁽⁶⁰⁾ scale will be used to subjectively record pain during LA injection and extraction. It consists of three schematic faces with different facial expressions for happy and sad faces representing: (A) satisfaction; (B) indifference; and (C) dissatisfaction, respectively. Each child will be trained to use the scale by modelling and then asking each participant to think of the last time she/he felt something painful and to select the facial expression that best represented his/her experience of discomfort.

[figure not shown]

Figure (4): Faces scale modified from the Maunuksela et al scale.

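### CC-ILA children with pain are switched to IANB, but the plan does not say which attempt is scored, in which group they count, or that the switch is an outcome

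*Combined protocol and SAP*

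**What the plan says.** All references are to the combined protocol and SAP.

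- **Clinical Procedure, Local Anaesthesia Administration:** "If the patient suffered pain at any given time in the experimental group, the procedure will be abandoned immediately, IANB will be administered", and the extraction is then completed. The rule covers the experimental group only. Before extraction the gingiva is probed "till full numbness is declared and the time of onset of the anaesthetic effect will be noticed".
- **Study Outcomes, objective method:** the SEM scale "will be used as an objective method for pain assessment during LA administration and extraction". Each child is "evaluated independently by a blind impartial observer using the recorded video tapes". On what is graded: "The slightest manifestation of the sound, eyes, or motion of the patient is graded in four levels". Nothing is said about an interrupted or repeated extraction.
- **Study Outcomes, physiologic method:** "Readings will be recorded at 2-minute intervals and the mean heart rate measurement will be calculated".
- **Study Outcomes, list:** pain reaction (heart rate, SEM, face scale) and adverse events at 24 hours. A switch or anaesthetic failure is not listed.
- **Statistical Analysis:** descriptive summaries, tests, software and significance level. There is no analysis population and no rule for switched children.
- **Sample size estimation:** 25 per group, "to compare the effectiveness of CC-ILA technique versus IANB during extraction of primary mandibular molars".

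**The concern.** The primary aim is whether CC-ILA eliminates extraction pain as compared with IANB. A CC-ILA child who feels pain is a failure on that aim. The child then receives the comparator, and the tooth comes out under both techniques. If the later, rescued extraction supplies the score, the failure is replaced by a score that IANB helped to produce. If the child is dropped, the failure disappears. Neither can happen in the IANB arm, which has no rescue.

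The trigger applies at any time, so it also covers the period before forceps are applied. A child switched then can only have an extraction score under CC-ILA plus IANB. The mean of 2-minute heart rate readings can likewise mix the periods before and after rescue. Because the switch is not an outcome, the report need not show how often any of this happened.

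**Working it through.** **1. The plan's own figure.** Inputs from Sample size estimation: SEM 3.93 (SD 1.223) for ILA, 5.17 (SD 1.891) for IANB, alpha 5%, power 80%. Two-sided, n = 2·SD²·(1.96 + 0.8416)²/Δ², with Δ = 5.17 − 3.93 = 1.24.
- Mean SD 1.557: 2 × 2.424 × 7.849/1.538 = 24.7, so 25.
- Root-mean-square SD 1.592: 2 × 2.536 × 7.849/1.538 = 25.9, so 26.

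The stated 25 reproduces. The section does not say whether these are injection or extraction scores. The Introduction reports the source's result "during both injection and extraction periods of mandibular primary teeth". I use them as extraction scores, as the sizing does.

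**2. Model.** Simulated trials, 25 v 25, scores on 3 to 12, two distribution shapes matched to the planning mean and SD. A CC-ILA child is switched when the first-attempt SEM reaches a trigger. The triggers are assumptions. The post-rescue score is an IANB score, at first independent of the first attempt. Differences are CC-ILA minus IANB, so a negative value favours CC-ILA.

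**3. Equal techniques, both arms at 5.17, zero correlation.**

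| Rule | ≥9 (6% switched) | ≥8 (12–13%) | ≥7 (23–24%) |
|---|---|---|---|
| Abandoned attempt scored | about 0; 5% | about 0; 5% | about 0; 5% |
| Post-rescue score only | −0.24 to −0.28; 7–8% | −0.44 to −0.47; 14–15% | −0.65; 27% |
| Switched children dropped | −0.25 to −0.29; 7–8% | −0.50 to −0.54; 15–17% | −0.84 to −0.86; 37–38% |

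Percentages after the semicolon are t-test rejection rates. Mann-Whitney with post-rescue scores rejects in 6%, 10% and 19–20%.

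Hand check at ≥7: with share p = 0.235, a bias of −0.65 means that switched children stood 0.65/0.235 = 2.77 points above the mean. Dropping them gives −(0.235/0.765) × 2.77 = −0.85, which agrees.

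**4. Correlation between a child's two attempts** (≥7, post-rescue scoring). Roughly, the bias shrinks by the factor (1 − r): 0.5 × 0.65 = 0.33 and 0.3 × 0.65 = 0.20. Simulated: −0.35 with 10% rejection at r = 0.5; −0.22 with 7% at r = 0.7.

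**5. Both arms at 3.93 (SD 1.223), post-rescue scoring, zero correlation.** Trigger ≥7 switches 4–5% and gives −0.15 to −0.17 with 7% rejection. Trigger ≥5 gives 32–36% rejection.

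**6. Planning means (true difference −1.24), post-rescue scoring, zero correlation.** The difference is −1.25 to −1.40 at ≥5 to ≥9, and −1.08 to −1.14 at ≥4. The largest shift is 1.40 − 1.24 = 0.16 one way and 1.24 − 1.08 = 0.16 the other. This limit belongs to zero correlation. Switched children are the high scorers, so a positive correlation raises their rescue scores and moves the difference towards zero; at low triggers the shift in that direction can then pass 0.16.

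**7. A rule that works the other way.** If the worse of the two attempts is scored and mild pain triggers the switch (≥4, 74–78% switched), equal techniques give +0.48 to +0.56 against CC-ILA, with 13–16% rejection.

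**The case against.** The strongest reply is that the harmful rules are hypothetical. Nothing in the text drops a child or moves one between groups; the groups are defined by assignment, and CONSORT is adopted for set-up and reporting. Grading the slightest sign on the video can be read as scoring the whole recording, abandoned attempt included, and under that rule the bias is about 0. Numbness is confirmed before extraction, so switches may be few. The 27% figure also needs zero correlation and a CC-ILA mean as high as 5.17; a child who has just been hurt and injected again may well react strongly again.

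Most of this stands. It limits the size and removes any claim that the plan as written is biased. It does not close the gap. A permissive reading is not a rule, and it gives no CC-ILA-only extraction score to a child switched before forceps. CONSORT does not settle which attempt is scored. If CC-ILA plus IANB numbs better than IANB alone, the bias could also be larger than shown.

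A reader might infer that the trial will favour CC-ILA, that the false-positive rate is 27%, or that the scoring rule will be picked once results are known. The documents support none of these. They give no switch rate or pain threshold, and they do not say when the rule is chosen. The flow chart and some closing pages were not available in the text, so a rule stated there cannot be excluded.

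**Conclusion.** The concern holds as an open rule that bears on the primary comparison, not as a demonstrated bias. The one-arm switch is explicit, and the available text leaves unsaid which attempt is scored, which group counts and whether switches are reported. With equal techniques and post-rescue scoring, false rejection ranges from about nominal (few switches, or strongly correlated attempts) to 26–27% at ≥7 with both arms at 5.17, and 32–36% at ≥5 with both arms at 3.93, these last two at zero correlation. If CC-ILA is as much better as planned, post-rescue scoring matters much less at zero correlation. All sizes rest on assumed triggers, assumed distribution shapes, an assumed correlation, and the planning scores being extraction scores. It should be settled before analysis.

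**What to change.** Keep the clinical rescue. Add to Study Outcomes and Statistical Analysis:

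1. All children are analysed as randomised; none is dropped for a switch.
2. Extraction SEM is scored from the existing video, from first forceps application up to abandonment. A child switched before forceps stays in the CC-ILA group with the completed-extraction score and a flag.
3. Injection scores come from the allocated injection only.
4. A pain criterion set in advance (for example SEM Sound grade 3) is coded from video in both arms. It is reported as anaesthetic failure per arm with a confidence interval, together with the number of CC-ILA children switched before and after forceps.
5. As a sensitivity analysis only, children meeting the criterion in either arm get the worst rank, with a Mann-Whitney test. With equal techniques this rejects in 4.4–4.9%. At the planning means its power is 71–75% at ≥7 to ≥9, against 72–76% with pre-rescue scores, but it falls to 50–56% at ≥4.
6. Extraction heart rate uses readings before rescue where they exist; otherwise the recorded mean is kept with a flag. Requiring a pre-rescue reading would lose children with pain from the CC-ILA arm only.
7. The face score refers to the completed extraction, with switched children flagged.

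**Cost.** A short paragraph and coding of the criterion from video in the control arm as well; no new measurement. CC-ILA may look less favourable. Some bias remains:

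- *Switches before forceps:* if half of switches come then, about −0.38 points and 11–12% rejection at ≥5 or ≥6 (both arms at 5.17, zero correlation).
- *Early stopping:* if stopped children score 1 point too low, the bias equals the switched share, −0.13 at ≥8 to −0.24 at ≥7, with 5–7% rejection. Rejection rises to 11–13% at ≥6 and 20–22% at ≥5.

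Failure counts at 25 per arm are for estimation only: Fisher power at the planning means is 31–37% at ≥7 and 7% at ≥8.

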Method: The study will be a double-blind randomized controlled clinical trial, parallel design. A total of 50 healthy children aged 5-7 years, will be selected from Pediatric Dentistry and Dental Public Health Department, Faculty of Dentistry, Alexandria University, Egypt. Children will be selected with scores 3 or 4 Frankl behavioral rating scale. Each child selected will have at least one mandibular primary molar that is indicated for extraction. Written informed consent will be obtained from guardian. Participants will be randomly allocated into two groups according to the technique of anesthesia that will be used. Group I (test group) will receive CC-ILA, while group II (control group) will receive IANB. Heart rate will be used as vital parameter of pain, and will be recorded at base line, during injection and during extraction procedure. Pain reaction will be assessed objectively by two investigators using Sensory, Eye, Motor (SEM) scale, while subjectively the pain will be evaluated by asking the child to express his experience using a modified face scale from the Maunuksela scale.

Results: Data will be collected, tabulated and statistically analysed to obtain the results and conclusions of this study.

Keywords: Computer – controlled, Intraligamentary, Local anesthesia, Nerve block, Articaine, Pain, Extraction.

INTRODUCTION

Child management is a primary challenge facing pediatric dentists routinely. Uncooperative behaviour can significantly affect treatment quality, time, and increase the possibility of child injury during treatment as mentioned by Ingersoll and Ingersoll.⁽¹⁾ Acknowledgement of various behaviour management techniques, operating skills, and most importantly providing profound local anaesthesia are critical to deliver high quality dental service.⁽²⁾

Local anaesthetic (LA) forms the backbone of pain control techniques in dentistry. Although it is considered one of the painful procedures in daily dental practice, especially for children, however, its obligatory to use LA to eliminate pain during the various dental procedures and maintain child cooperation during the dental session.

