- In the experimental group, CC-ILA will be administered using the Wand-STA system according to the manufacturer instructions, which is also concurrent with Mittal and Chopra (2019)⁽³⁰⁾. It works with standardised 1.8 mL local anaesthetic carpules. The distolingual and mesiolingual line angles are the most effective for multi-rooted mandibular teeth.
- The injection is initiated by activating the STA mode when the foot control is tapped. A 30-gauge ultra-short disposable dental needle will be inserted in the PDL through the gingival sulcus at the distolingual line angle of the target tooth first, guided by constant audible tones and visual feedback. The needle should be directed approximately 30° angle to the long axis of the tooth and the bevel facing the alveolar bone. A total of 0.9 mL Articaine hydrochloride 4% with 1:100,000 epinephrine will be injected for each root as shown on a special indicator.
- During the anaesthetic solution delivery, the visual pressure indicator will be observed as the pressure is increasing from the red into the green zone. Tissue blanching may occur, which

suggests that enough LA has been delivered. Injection will be stopped by lightly tapping the foot pedal again. The dentist will wait 5 seconds before needle withdrawal. Same steps will be repeated at the mesiolingual line angle.⁽³¹⁾

b) Conventional technique:

- In the control group, a standard technique for the Inferior Alveolar Nerve Block (IANB) will be used supplemented with long buccal infiltration for the buccal gingiva. While the mouth is open as wide as possible, the index finger palpates the injection site.
- A 27-gauge disposable dental needle will be used to inject Articaine hydrochloride 4% with 1:100,000 epinephrine. The needle will be directed between the two primary molars on the opposite side of the arch, entering the tissues at the level of the occlusal plane or slightly lower until bony resistance is met.
- The needle is withdrawn 2mm to aspirate. Once negative aspiration is checked, the remainder of the solution is slowly deposited. The lip and/or cheek will be shaken as a method of distraction. Approximately 1.0 mL of LA will be delivered near the inferior alveolar nerve.⁽³⁶⁾ Two-thirds the needle length should be inserted.
- The needle is withdrawn, then 0.5 ml as a long buccal infiltration distal to the second primary molar is administered.⁽⁵⁵⁾

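### Heart rate is a mean of 2-minute readings not tied to needle entry or luxation, so a brief pain response can go unsampled or be diluted

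*Combined protocol and SAP*

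**What the plan says.** In Study Outcomes, part A (Physiologic method), a pulse oximeter gives a baseline heart rate before the anaesthetic. Then "another measurement will be recorded during LA administration, and during extraction". The next sentence sets the sampling rule: "Readings will be recorded at 2-minute intervals and the mean heart rate measurement will be calculated". The Abstract lists the same three time points, saying that heart rate "will be recorded at base line, during injection and during extraction procedure".

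The plan does not state the start of the 2-minute clock, the number of readings per phase, or whether the mean is per phase or over the whole visit. The Statistical Analysis section lists t-, paired t-, Wilcoxon signed-rank and Mann-Whitney tests. It names no peak, no event reading and no change from baseline for heart rate, and no between-arm comparison that uses the baseline.

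The two injections differ in steps (Local Anaesthesia Administration). For CC-ILA: "A total of 0.9 mL Articaine hydrochloride 4% with 1:100,000 epinephrine will be injected for each root", and "The dentist will wait 5 seconds before needle withdrawal. Same steps will be repeated at the mesiolingual line angle". For IANB: "Approximately 1.0 mL of LA will be delivered near the inferior alveolar nerve", "then 0.5 ml as a long buccal infiltration distal to the second primary molar is administered". Neither arm has a stated injection time or flow rate.

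**The concern.** Heart rate is one of three pain measures, and it is meant to show the child's reaction to the needle and to the forceps. Those reactions may be short. A reading taken by the clock meets them only by chance. If the phase is long enough for several readings, the one that catches the reaction is averaged with others that do not.

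Two teams following this text could also produce different outcomes. One might start the clock at needle entry and the other at seating; one might average within each phase and the other across phases. If injection times differ between arms, the averaging could act more strongly in the longer technique, so part of a heart-rate difference could reflect duration and not pain.

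**Working it through.** **The plan's own figure.** The plan gives no heart-rate SD, target difference or phase length. Its only design figure is 25 per group, from SEM means of 3.93 (SD 1.223) and 5.17 (SD 1.891), alpha 5% and power 80%. With two-sided alpha (assumed), n = 2 × (1.960 + 0.842)² × SD² / 1.24². The average SD of 1.557 gives 24.75, so 25; the root-mean-square SD of 1.592 gives 25.9, so 26. The figure reproduces, and heart rate plays no part in it.

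**Inputs from the plan.** Readings 120 s apart, averaged. CC-ILA 2 × 0.9 = 1.8 mL, with a 5 s wait at each of two sites. IANB 1.0 + 0.5 = 1.5 mL.

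**Assumptions.** One response of height H = 10 beats/min and length S = 30 s, starting at needle entry; phase length D; and either a free-running clock (random offset from the injection) or an anchored clock (first reading at the start of injection).

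**Step 1: chance that the response is sampled, free-running clock.** S/120 = 30/120 = 25%, or about 6 of 25 children per arm. For a 20 s response it is 17%, and for 10 s it is 8%.

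**Step 2: expected rise in the phase mean, free-running clock.**
- D = 120 s: one reading, so 0.25 × 10 = 2.5 beats/min.
- D = 180 s: the response is caught only if the first reading falls in the first 30 s. The next reading, 120 s later, is then still inside the phase. The rise is 0.25 × 10/2 = 1.25.
- D = 240 s: always two readings, so again 1.25.
- D under 120 s, given one reading at an arbitrary moment: H × S/D, which is 5.0 at 60 s and 3.3 at 90 s.

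The shortcut H × S/D would give 1.7 at 180 s, but it does not hold beyond 2 minutes for a response at needle entry. As a check on the assumed shape, a 20 beats/min response lasting 20 s gives (20/120) × 20 = 3.3 at 2 minutes and 1.7 at 3 to 4 minutes.

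**Step 3: anchored clock.** Readings fall at 0, 120 s and so on, so their number is k = D/120 rounded up. A response present at the opening reading has weight 1/k: 1 up to 120 s, and 1/2 at 180 to 240 s.

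**Step 4: could the arms differ?** At an equal assumed rate of r seconds per mL, IANB takes 1.5r and CC-ILA takes 1.8r + 10. Time to move between sites is left out in both arms.

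| r (s/mL) | IANB (s) | CC-ILA (s) | Ratio | Expected rise, free-running, IANB v CC-ILA (given a reading) |
|---|---|---|---|---|
| 30 | 45 | 64 | 1.42 | 6.7 v 4.7 |
| 60 | 90 | 118 | 1.31 | 3.3 v 2.5 |
| 120 | 180 | 226 | 1.26 | 1.25 v 1.25 |

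On the anchored clock the two arms have the same number of readings in every row (one, one, two), so the dilution is equal. An arm difference therefore depends on the clock and on durations that the plan does not give.

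**The case against.** The strongest reply is that the two sentences can be read together: at least one reading in each phase, repeated every 2 minutes if the phase runs longer, then averaged. On that reading every child has an injection value.

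This answers one stronger claim that a reader might infer, namely that a short injection could leave no reading at all. A free-running clock alone would give no reading in 1 − 60/120 = 50% of 60 s injections. But both the Abstract and the physiologic method require a measurement during injection and during extraction, so the documents do not support that claim.

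A reader might also infer a bias towards a particular arm, perhaps fourfold, by setting a 1-minute phase (5.0) against a 4-minute phase (1.25). The documents support neither. They give no times or flow rates and do not say which technique is slower. At equal rates the volumes give a ratio of only about 1.3 to 1.4.

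Three further points stand. The volume argument concerns injection only: extraction, the subject of the primary aim, is done the same way by the same operator in both arms. Discomfort lasting through the injection, or recurring at the second needle entry, would be diluted less than the single response assumed here. SEM and the faces scale cover both phases and do not depend on this sampling.

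What the reply does not remove is that even a required reading in each phase may fall at any moment of it, and that the stated summary is still a mean over clock times.

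**Conclusion.** The point holds as a weakness in how a supporting outcome is measured. The sampling rule is not tied to the painful events, its start and unit of averaging are undefined, and nothing in the analysis section compensates.

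On a free-running clock, a 30 s response at needle entry is sampled in about a quarter of children once the phase lasts 2 minutes. A 10 beats/min rise then contributes 2.5 beats/min to the phase mean at 2 minutes and 1.25 at 3 to 4 minutes. The height, length and position of the response, the phase lengths and the clock are all assumptions.

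A difference between arms is possible, not shown. If equal flow rates are assumed, CC-ILA would be the longer injection. There would be no differential dilution if the clock starts with the injection and both injections last under 2 minutes. The SEM-based sample size is untouched.

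**What to change.** Replace the 2-minute mean with readings at the same named events in both arms: baseline, first needle entry, second needle entry, first luxation and tooth delivery. Each arm has two needle entries, so neither gets more chances at a high value.

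Define the phase value in advance, for example the higher of the two event readings in each phase. Compare arms on that value with baseline heart rate as a covariate, in place of an unadjusted two-group test. The baseline is already collected.

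Have the readings noted by the assistant already present (the operator, per the Clinical Procedure section, is one "who will be assisted by a trained dental assistant"). The Blinding section, which gives heart-rate recording to the operator, would need to match.

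The cost is protocol wording, one analysis line and a five-box record form, with no new device or staff. The downside is that event readings are noisier than a mean and more exposed to movement artefact, which matters because the protocol itself asks the child to keep still for accurate readings.
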